
regulate expression of numerous genes. Interestingly, digoxin does not alter PKM2 kinase activity but suppresses PKM2 dependent transcriptional activity. This area is significant because sterile inflammation (SI) is the central pathological process in AH. Our results identify PKM2 as a key molecule in liver sterile inflammation which can be therapeutically targeted. The identification of digoxin as a PKM2 binder, which leads to critical anti-inflammatory effects, provides a novel opportunity to reduce liver inflammation in AH. We have further identified a unique molecular profile from a pilot aptamer-proteomic screen which will be expanded to the whole InTeam cohort to provide predictive markers for severe AH.

4. **Research Plan:** Summarize the study design and research procedures using non-technical language that can be readily understood by someone outside the discipline. **Be sure to distinguish between standard of care vs. research procedures when applicable, and include any flowcharts of visits specifying their individual times and lengths.** Describe the setting in which the research will take place.

Test if administering digoxin orally to healthy subjects results in a reduction in innate immune inflammatory responses in the peripheral blood.

We need to obtain peripheral blood lymphocytes from healthy subjects on different doses of digoxin to test if digoxin has an effect on the immune response of PBLs.

A) There will be three study groups.

Groups:

A: Placebo n=15

B: Digoxin 3 mcg/Kg/day n=15

C: Digoxin 0.15 mcg/Kg/day n=15

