Serum digoxin concentrations, BUN, Creatinine, CBC, Electrolytes (Na, K) and ECGs will be obtained weekly. pregnancy testing for female participants of childbearing potential and a baseline screening to determine if you are eligible for this study. Peripheral blood (25ml) in EDTA tubes (purple top) will be obtained at 0, 1, 2, 3 weeks after starting digoxin, with written consent and in accordance with the guidelines of Yale University ethics committee. PMN and monocytes will be isolated using PolymorphPrep (Axis-Shield) according to standard procedure, and purity will be determined by flowcytometric analysis. Spontaneous ROS of PMNs will be measured by culturing neutrophils with CM-H2DCFDA for 30 minutes, washing, followed by kinetic analysis of intracellular ROS with fluorescent plate reader. Neutrophils up-regulate ROS spontaneously in culture, and for each sample the untreated aliquot will be the control for the digoxin treated aliquot. Monocytes will be stimulated LPS (100ng/ml) for 3 hrs after which cDNA will be prepared and qPCR conducted for IL-1B, TNF- α and IL-6. cDNA and supernatant will be stored for further analysis based on initial results.

These initial numbers are based the use of similar assays in the preliminary data. We will obtain additional assistance from [name] Professor of Biostatistics at the University of Massachusetts, who will 1) review of study design, including sample size and specimen utilization; 2) develop an appropriate data management system to provide data capture and edit capabilities; 3) develop appropriate statistical analysis, quality assurance, and quality control plans; 4) conduct the statistical analysis and provide material for presentation/publication; and 5) provide resources to assure reproducible research. Please see letter of support.

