B) The data management system will be set up in the University of Massachusetts Medical School secure REDCap environment, which is used for all of the pilot studies funded by NIAAA as part of the AlcHepNet Research Network. This HIPAA-compliant, 21 CFR Part 11 compliant environment is accessible only by medical school staff and collaborating clinical sites of the AlcHepNet who are assigned an account in this environment by UMMS IT with approval by the UMMS IRB. The system will be programmed for a single entry with validation rules at the time of entry and additional checking conducted after the data have been submitted to the main data base. These edits will check for validity, consistency, and normal range values. Edit queries will be generated and resolved by clinic staff with corrections posted to the database through the REDCap system, which enforces an audit trail for all changes. The study database will be stored in REDCap within the secure environment to protect any PHI/PII data

that are collected as part of the study. We will strive to minimize collection of such data and REDCap will be programmed to segregate that data from the study data so that exports for analysis will be deidentified. Data will be exported from REDCap for import into the latest version of SAS (SAS Institute, Cary, NC) or other statistical software for all analysis.

C-E) All reports and analyses will be generated from these files. Data files (and accompanying programs) that are used for reports, presentations, or publication will be archived as required past the end of the study. REDCap will also have the audit trail capability enabled for tracing any data modifications. Data from laboratories can be uploaded directly into REDCap for storage. The REDCap system will be programmed and maintained by study staff at the U Mass Medical School AlcHepNet Data Coordinating Center while data entry will be performed by study staff at the local site.

The sample size for this pilot study was based on results from in vitro experiments, where differences in as few as 5 participants were seen to be significantly different. Given the inherent variability in the absorption of digoxin in humans, a sample size of 15 was determined to be reasonable to provide a reasonable distribution of results from repeated measures of participants at the differing digoxin dose levels.

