F) Pregnancy: *The chance of a female subject to become pregnant on a 4-week study is very less, if in case this does happen they will be asked to stop the drug and withdraw from the study immediately. We do not intend to follow the pregnancy and birth outcome.*

Drug preparation: Digoxin is commercially available as a 0.05mg/ml elixir (Boehringer Ingelheim). The appropriate dosing of digoxin and control will be prepared with the help of the Yale Center for Clinical Investigation (YCCI) as detailed in the facilities and resources. Stopping criteria: Subjects will be removed from the study if any serum digoxin level is above 0.8ng/ml, or if there are any abnormalities in blood tests or ECGs. Data from these subjects will not be used in the analysis. Analysis, expected outcome and alternative approaches: It is expected that there will not be a significant difference in the neutrophil ROS and monocyte qPCR results in control group A between the four time points. It is expected that for group B and C, both neutrophil ROS and monocyte qPCR levels will be lower at time points 1, 2, 3 weeks as compared to time 0, and as compared to all time points of group A. It is not clear if in group D time points of week 1, 2, and 3 will be any different from time point 0. For the time points where significant differences are found we will perform additional luminex assay with the supernatant using the luminex five plex panel (GM-CSF, IL-1B, IL-6, IL-8, TNF- α). There will also be an analysis of the production of ROS and qPCR levels in relation to serum digoxin levels at the time that the analysis samples were obtained. The combinations of these analysis will establish that digoxin taken orally is effective in reducing inflammatory responses, and will also provide information on dose response for oral dosing as well as serum concentrations.

5. Genetic Testing N/A

A. Describe

- i. the types of future research to be conducted using the materials, specifying if immortalization of cell lines, whole exome or genome sequencing, genome wide association studies, or animal studies are planned *Write here*
- ii. the plan for the collection of material or the conditions under which material will be received *Write here*
- iii. the types of information about the donor/individual contributors that will be entered into a database *Write here*
- iv. the methods to uphold confidentiality *Write here*

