- B. What are the conditions or procedures for sharing of materials and/or distributing for future research projects? *Write here*
- C. Is widespread sharing of materials planned? *Write here*
- D. When and under what conditions will materials be stripped of all identifiers? *Write here*
- E. Can donor-subjects withdraw their materials at any time, and/or withdraw the identifiers that connect them to their materials? *Write here*
 - i. How will requests to withdraw materials be handled (e.g., material no longer identified: that is, anonymized) or material destroyed? *Write here*
- F. Describe the provisions for protection of participant privacy *Write here*
- G. Describe the methods for the security of storage and sharing of materials *Write here*

6. **Subject Population:** Provide a detailed description of the types of human subjects who will be recruited into this study.
In total 60 healthy subjects ≥18 years and ≤70 years with no known clinical history will be recruited for this study.

7. **Subject classification:** Check off all classifications of subjects that will be specifically recruited for enrollment in the research project. Will subjects who may require additional safeguards or other considerations be enrolled in the study? If so, identify the population of subjects requiring special safeguards and provide a justification for their involvement.

 Children	 Healthy	 Fetal material, placenta, or dead fetus
 Non-English Speaking	 Prisoners	 Economically disadvantaged persons
 Decisionally Impaired	 Employees	 Pregnant women and/or fetuses
 Yale Students	 Females of childbearing potential	

NOTE: Is this research proposal designed to enroll children who are wards of the state as potential subjects?
 Yes No

8. **Inclusion/Exclusion Criteria:** What are the criteria used to determine subject inclusion or exclusion?

Inclusion Criteria

1. *Age >18 y ≤ 70 years*
2. *subjects with normal serum creatinine, normal EKG and currently not taking any medication.*

Exclusion criteria

1. *Autoimmune liver disease (ANA > 1/320)*
2. *Chronic viral hepatitis*
3. *Hepatocellular carcinoma*
4. *Complete portal vein thrombosis*
5. *Extrahepatic terminal disease*
6. *Pregnancy*

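### Dropping all data from subjects removed for a digoxin level above 0.8 ng/ml makes inclusion in the dose comparison depend partly on exposure

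*Combined protocol and SAP*

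**What the plan says.** Part F of the Research Plan (Section I, item 4) gives the condition for a subject to leave: "removed from the study if any serum digoxin level is above 0.8ng/ml, or if there are any abnormalities in blood tests or ECGs". The next sentence is "Data from these subjects will not be used in the analysis". It makes no exception for samples taken before removal.

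The same item sets the timing. For safety tests, "Serum digoxin concentrations, BUN, Creatinine, CBC, Electrolytes (Na, K) and ECGs will be obtained weekly". The research blood for ROS and qPCR "will be obtained at 0, 1, 2, 3 weeks after starting digoxin". There are three groups of 15: placebo, 3 mcg/kg/day, and "Digoxin 0.15 mcg/Kg/day n=15". Part F also plans an "analysis of the production of ROS and qPCR levels in relation to serum digoxin levels".

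Statistical Considerations (Section I, item 13) specifies a mixed model with dose, categorical week, age, gender and a random intercept. It defines no analysis population, missing-data rule or sensitivity analysis, so nothing there overrides part F.

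**The concern.** A level above 0.8 ng/ml can only be seen after dosing starts, and it is a consequence of the dose. Excluding on it selects subjects by something the treatment causes, and does so unevenly. The 3 mcg/kg/day group can lose its most exposed members, while the other two groups lose practically none by this route. If digoxin lowers ROS and qPCR more at higher levels, the subjects left in the 3 mcg/kg/day group show less effect than the full group would.

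Three further costs follow.

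- **Valid data are discarded.** A subject removed at week 3 would lose up to four samples that had already been drawn, although the mixed model can use an incomplete series.
- **Numbers fall.** The number analysed can drop below 15 per group, and the plan does not say that removed subjects are replaced. The sample-size paragraph cites variable absorption as a reason for its number ("Given the inherent variability in the absorption of digoxin in humans, a sample size of 15 was determined to be reasonable"), yet the rule cuts off the upper end of that variability.
- **The exposure range narrows.** The planned analysis against serum level loses its highest levels, which costs precision.

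The blood-test and ECG triggers differ. Entry requires "subjects with normal serum creatinine, normal EKG and currently not taking any medication", but a later abnormality can occur in any group, so these triggers mainly cost numbers.

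**Working it through.** The plan gives no figure to reproduce here: no expected level, variability, removal rate, effect size or power. What follows is an illustration.

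**From the documents:** threshold 0.8 ng/ml; 15 per group; doses 3 and 0.15 mcg/kg/day, ratio 3/0.15 = 20; weekly levels; research samples at weeks 0 to 3; pairwise significance level 0.05/3.

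**Assumed:** lognormal levels in the 3 mcg/kg/day group, median m from 0.3 to 0.7 ng/ml, between-subject coefficient of variation (CV) 30% or 50%; levels proportional to dose.

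**Step 1. Constant level per subject, effect proportional to level.** Let s = √ln(1 + CV²) and k = ln(0.8/m)/s. The excluded share is 1 − Φ(k). The share of the full-group effect retained is Φ(k − s)/Φ(k). For m = 0.5 and CV 50%: s = √ln 1.25 = 0.472; k = 0.470/0.472 = 0.995; excluded 16.0%, or 0.160 × 15 = 2.4 subjects; retained Φ(0.523)/Φ(0.995) = 0.699/0.840 = 0.83.

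| Median (ng/ml) | CV 30%: excluded (of 15) | retained | CV 50%: excluded (of 15) | retained |
|---|---|---|---|---|
| 0.3 | 0.04% (0.0) | 0.999 | 1.9% (0.3) | 0.964 |
| 0.4 | 0.9% (0.1) | 0.990 | 7.1% (1.1) | 0.904 |
| 0.5 | 5.5% (0.8) | 0.957 | 16.0% (2.4) | 0.832 |
| 0.6 | 16.4% (2.5) | 0.901 | 27.1% (4.1) | 0.761 |
| 0.7 | 32.5% (4.9) | 0.835 | 38.9% (5.8) | 0.695 |

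With medians divided by 20, exclusion by level at 0.15 mcg/kg/day is at most about 2 × 10⁻¹¹.

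**Step 2. Any of three weekly levels can trigger.** With a within-subject CV of 20% added (simulated), exclusions are about 0.1 to 0.8 of 15 at median 0.3, 2.7 to 4.1 at 0.5, and about 8 at 0.7. The mean level among those kept is 92-99%, 76-89% and 62-74% of the full-group mean.

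**Step 3. Saturating effect.** Take effect = level/(level + h) with a constant level per subject, where h is the level giving half the maximal effect. Over the ten settings of Step 1, retention is 86-100% with h at the 3 mcg/kg/day median, 95-100% with h at one fifth of it, and 98.6-100% with h at one twentieth of it (the 0.15 mcg/kg/day median).

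**Step 4. Loss of numbers.** For a 1.0 SD difference from 15 placebo subjects at one time point, approximate power is Φ(1/√(1/15 + 1/n) − 2.394), where 2.394 is the two-sided critical value at 0.05/3. For n = 15: Φ(2.739 − 2.394) = 0.64. For n = 12: Φ(2.582 − 2.394) = 0.58. For n = 10: Φ(2.449 − 2.394) = 0.52.

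**Step 5. Blood-test and ECG triggers.** If q results per visit are each abnormal by chance with probability p, independently over three visits, the share with at least one is 1 − (1 − p)^(3q). For q = 5, p = 1% this is 14%; for q = 10, p = 5% it is 79%. This operates in every group.

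**Step 6. Analysis against serum level.** In simulated trials with a true linear slope of −1 (15 per group, one observation each), the mean slope is −1.00 with and without the subjects above 0.8 ng/ml. Dropping them multiplies its standard error by 1.00-1.06 at median 0.3, 1.08-1.36 at 0.5 and 1.45-1.92 at 0.7.

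**The case against.** The strongest objection concerns size. The largest loss in Step 1, about 30% of the effect, needs the highest median, the wider CV and an effect proportional to level. Part F itself expects ROS and qPCR to fall in both digoxin groups. A visible effect at one twentieth of the dose fits a saturating curve better, and then little is lost. The drug background (Section II, part B, item 2) also says that the dose was chosen to keep levels at or under the therapeutic range. It does not tie that range to 0.8 ng/ml, but it suggests few removals; at medians of 0.3 to 0.4, Step 1 gives 0 to about 1 of 15. This stands, and it makes the size uncertain. It does not justify the sentence: the sponsor cannot know beforehand which case applies, and no analytic benefit is stated.

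On numbers, the plan targets 60 subjects (Section I, item 6; Section III, item 1) against 3 × 15 = 45 in the groups. The extra 15 might cover losses, but their purpose is not stated; they may go with the group D that part F mentions and the group list omits.

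Stronger readings are tempting but unsupported.

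- *The serum-level analysis is biased.* Excluding on the explanatory variable does not by itself bias a correctly specified slope; precision is lost.
- *All triggers are dose-linked.* Blood-test and ECG abnormalities can arise on placebo too.
- *Removed subjects vanish from the safety summary.* The plan does not say so. Adverse events are recorded at each weekly visit and reviewed as each subject finishes.

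**Conclusion.** The point holds. The exclusion is stated without qualification, nothing overrides it, and it acts almost only on the 3 mcg/kg/day group through the level trigger. Confidence is high that the rule exists and that its bias runs towards no effect if the effect rises with level. Confidence in the practical consequence is medium at most.

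The size cannot be derived from the documents. Under the assumptions above, level-triggered exclusions are about 0 to 6 of 15 with a constant level per subject, or about 0.1 to 8 of 15 if any of three varying weekly levels can trigger. With a constant level, the retained share of the group's effect is 70-100% if proportional to level, and 86-100% if it saturates with half-maximal level at or below the group's median. The bias therefore runs from negligible to material.

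A reader might infer that the dose comparison is invalid, or that a loss near 30% is to be expected. The documents support neither, because they give no expected levels and no effect shape. Nor does the point bear on the removal threshold. It concerns only what is done with data already collected.

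**What to change.** Leave the removal rule unchanged. Replace the sentence that excludes the data with:

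> All ROS/qPCR data from samples taken up to and including the visit whose result triggers removal, with the week-0 sample, are analysed in the assigned group; the analysis against serum digoxin level uses all measured levels; removals are tabulated by group and reason.

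Tying the cut-off to the visit whose result triggers removal settles the case where a result comes back after the visit. Subjects found ineligible before any dose may be left out. An analysis without removed subjects may be kept, optionally, as a labelled sensitivity analysis.

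The plan should state that this reduces the bias but does not remove it: later samples are still missing because of digoxin level, which is not in the mixed model. In the worst proportional case (median 0.7, CV 50%, removal at week 1, within-subject correlation 0.3 or 0.7), simulated retention rises from 70% to 84-88% averaged over weeks 1 to 3, and to 77-82% at week 3.

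The cost is wording and slightly more analysis. The samples are already scheduled, so no subjects, visits or blood draws are added.

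### Section 4 rests its efficacy conclusion on within-group changes and off-week placebo comparisons; it should rest on the between-group difference in change from week 0

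*Combined protocol and SAP*

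**What the plan says.** The protocol describes three groups of 15: placebo (A) and two digoxin groups, "B: Digoxin 3 mcg/Kg/day n=15" and "C: Digoxin 0.15 mcg/Kg/day n=15". Research blood samples "will be obtained at 0, 1, 2, 3 weeks after starting digoxin".

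Section I, item 4, under Analysis, expected outcome and alternative approaches, sets out three pieces of evidence:

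1. Placebo: "It is expected that there will not be a significant difference in the neutrophil ROS and monocyte qPCR results in control group A", the comparison being "in control group A between the four time points".
2. Groups B and C against their own baseline.
3. Groups B and C against placebo.

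Pieces 2 and 3 come in one phrase: both outcomes are expected to be "lower at time points 1, 2, 3 weeks as compared to time 0, and as compared to all time points of group A". The paragraph then concludes: "The combinations of these analysis will establish that digoxin taken orally is effective in reducing inflammatory responses". It gives no test, no significance level and no rule for combining the pieces.

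Section I, item 13 (Statistical Considerations) makes the primary analysis a mixed model with dose, categorical time, participant characteristics and a random intercept. An omnibus test across the three groups comes first, followed by pairwise comparisons at 0.017. No dose-by-time term is named.

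**The concern.** Pieces 1 and 2 are separate within-group readings. A significant fall on digoxin beside a non-significant course on placebo does not test whether the two changes differ. With 15 people, non-significance does not show that placebo was stable. Piece 3 includes comparisons such as digoxin at week 3 against placebo at week 0, where treatment and time differ together.

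The outcomes are neutrophil ROS and LPS-stimulated mRNA, measured on cells freshly isolated at each visit. A shift after week 0 shared by all groups (assay, operator, season) is therefore plausible. The placebo group is there to remove such a shift, and within-group readings do not use it for that.

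Two things are at stake: what the trial may claim, and which samples get the follow-up Luminex assay. Item 4 assigns that assay to time points showing significance without saying which comparison counts.

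**Working it through.** **Inputs from the plan.** Three groups of 15; four visits (weeks 0 to 3); pairwise threshold 0.05/3 = 0.0167, printed as 0.017.

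**Assumptions, because the plan gives no figure.** Within-group tests at two-sided 0.05; total SD 1; ICC 0.5 and 0.7; no drug effect; a fall of the same size in all groups after week 0. The plan states no effect size, SD or power, so its sample size of 15 cannot be reproduced.

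**Step 1: exact check, week 3 against week 0 only.** Let p be the chance that a paired t test with n = 15 shows a significant fall. For a shared fall of 0.5 SD of the change score, the noncentrality is 0.5 × √15 = 1.94 and p = 0.438.
- One digoxin group falls, placebo does not: p(1 − p) = 0.438 × 0.562 = 24.6%.
- B or C falls, placebo does not: [1 − (1 − p)²](1 − p) = (1 − 0.316) × 0.562 = 38.4%.
- With no drift, the B-or-C figure is 4.7%. At a drift of 1.0 SD of change it is 5.1%, because placebo then usually turns significant too.

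**Step 2: simulation with all four visits.** 20,000 trials per scenario; placebo judged by a repeated-measures F test (3 and 42 df); B and C by week-versus-week-0 tests. Drift is in units of total SD.

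| Reading of item 4 | False credit, drift 0.3-0.5 SD, ICC 0.5-0.7 |
|---|---|
| Placebo non-significant; B or C below own week 0 at one or more weeks | about 31-56% |
| Same, but one group must fall at all three weeks | about 7-20% |
| One or more weeks, and mean numerically below every placebo mean | about 22-36% |
| One or more weeks, and significantly below same-week placebo | about 3-5% |
| One or more weeks, and significantly below every placebo time point | 2% or less |

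With no drift, the first row gives 11-12%, which is multiplicity over groups and weeks. At a drift of 0.8 SD it gives about 12% (ICC 0.5) and under 2% (ICC 0.7).

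**Step 3: between-group tests under the same drift.** The group main effect implied by item 13 rejects in 4.7-5.4% of null trials, and a dose-by-time F test in 4.6-5.5%. One averaged change contrast per dose (mean of weeks 1-3 minus week 0; B minus A or C minus A; each at two-sided 0.05, falls only) gives 4-5%. Testing the change at each week separately at 0.05, and accepting any week in B or C, gives about 11%.

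**Step 4: what the main effect estimates.** If digoxin lowers the outcome by δ at weeks 1-3 and by nothing at week 0, the group effect averaged over four visits is (0 + δ + δ + δ)/4 = 0.75δ. With σ = 1:
- SE of the main effect = √{[ICC + (1 − ICC)/4] × 2/15}
- SE of the change contrast = √{(1 − ICC) × (4/3) × 2/15}

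| ICC | Main effect, 0.75δ/SE | Change contrast, δ/SE |
|---|---|---|
| 0.3 | 0.75δ/0.252 = 2.98δ | δ/0.353 = 2.83δ |
| 0.5 | 0.75δ/0.289 = 2.60δ | δ/0.298 = 3.35δ |
| 0.7 | 0.75δ/0.321 = 2.33δ | δ/0.231 = 4.33δ |

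The two are equal at ICC = 1/3. Above that, the change contrast is the more sensitive.

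**The case against.** The strongest reply is that item 4 states expectations and item 13 states the inference. Item 13's primary test compares groups, and drift shared by all groups does not inflate it. Item 4 also joins the placebo comparison to the baseline comparison with an and: "as compared to time 0, and as compared to all time points of group A". It expects the pattern in both B and C, at weeks 1, 2 and 3, and on both outcomes. Requiring B and C to fall at all three weeks gives only 0.1-5% at drifts of 0.3-0.5 SD, even without the placebo comparison.

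Much of this stands. A reader might infer that the trial as planned would declare digoxin effective in about half of null trials. The documents do not support that. The figure needs the loosest reading (B or C, any week, one outcome, no placebo comparison), a moderate drift, and no regard for item 13.

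It does not dispose of the point. Item 4 makes an inferential claim, that the combined analyses will establish efficacy, and does not tie it to item 13. It says lower without saying whether that means numerically or significantly lower, and the answer moves the error from 22-36% to 5% or below. Item 13 does not fill the gap, because the terms it lists do not estimate the difference in change.

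**Conclusion.** The point holds as a defect in how item 4 combines evidence, together with a missing term in item 13. It is not a finding that the primary test has an inflated error rate.

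The within-group elements alone can credit a shared drift to digoxin in about 31-56% of null trials at one or more weeks, and about 7-20% at all three weeks. The placebo comparison may or may not repair this, because its meaning is left open. Drift size and shape, ICC and the within-group significance level are all assumptions, and the problem shrinks at both very small and large drifts. The change is worth making before analysis, at moderate priority.

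**What to change.** - **Item 4:** state that a digoxin effect is concluded only from the between-group difference in change from week 0 (B minus A, C minus A). Limit any comparison with placebo to the same week. Present each group's time course, placebo included, as descriptive estimates with confidence intervals. Say which comparison triggers the Luminex assay.
- **Item 13:** add the dose-by-time term and pre-specify one contrast per dose, for example the mean of weeks 1-3 minus week 0. Apply the existing sequence to that contrast: an omnibus test across the three groups, then pairwise comparisons at 0.017. Do not test each week separately at 0.05.

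**Cost.** Wording and model specification only, with no new data or participants. The between-group change has a larger SE than a within-group change, by √2 for equal groups (at ICC 0.5, 0.298 against 0.211 SD for the averaged contrast). If the ICC is as low as about 0.3, the contrast is also slightly less sensitive than the main effect.

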- Risks and Inconveniences of an electro-cardiogram (EKG): EKG is very safe procedure which is being performed very commonly for evaluation of cardiac status. There is no risk of performing EKG to the subjects, however, there may be slight inconvenience of cold sensations to the skin related to the application of gel at the site of EKG leads placement.

11. **Minimizing Risks:** Describe the manner in which the above-mentioned risks will be minimized.

1. Each participant will be enrolled only after signing an informed consent in the presence of a study coordinator. Participants will have adequate opportunity to review the informed consent and to ask any questions they may have about the research protocol, compensation, risks, and benefits of taking part in the study.
2. Blood draws and other biological sample collections will be performed by trained personnel. pregnancy testing for female participants of childbearing potential and a baseline screening to determine if you are eligible for this study.
3. A written detailed collection procedure is provided to minimize spilling during collection.
4. Serum digoxin concentrations, BUN, Creatinine, CBC and ECGs will be obtained weekly to monitor the adverse effect of digoxin. In case, subject is having adverse effect related to digoxin, they will be removed from study and medical care will be provided at Yale new haven hospital if needed.
5. In terms of potential drug allergies, all subjects will be asked standardized questions about previous allergic reactions to digoxin. If a participant reports a digoxin allergy, they will be excluded. We will contact (telephone, email, or text message) each participant within three days of starting the oral digoxin in order to assess tolerability.

6. There may be low risk of breach of confidentiality, however we will follow appropriate data safety plan to minimize the breach of confidentiality. In addition, unauthorized personnel will not be allowed to have access to subject's confidential information.

7. If study subjects express a desire to discontinue the protocol, for any reason, the intervention will be immediately terminated and consent to participate may be rescinded at the subject's discretion.

12. Data and Safety Monitoring Plan: Include an appropriate Data and Safety Monitoring Plan (DSMP) based on the investigator's risk assessment stated below. (Note: the HIC will make the final determination of the risk to subjects.)

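### Enrolment is set at 60, but the three defined groups hold 45, and the plan refers to a group D that it never defines

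*Combined protocol and SAP*

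**What the plan says.** All references are to the combined protocol and SAP.

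- **Total.** Section I, item 6 (Subject Population): "In total 60 healthy subjects" are to be recruited. Section III, item 1 (Targeted Enrollment) also gives 60 for the single site. The multi-site questions are marked not applicable or left unanswered, so no other site accounts for the difference.
- **Groups.** Section I, item 4 (Research Plan): "There will be three study groups". These are A (placebo), B (digoxin 3 mcg/kg/day) and C (digoxin 0.15 mcg/kg/day), each with n=15.
- **Sample size.** The same item gives the rationale that "a sample size of 15 was determined to be reasonable". It gives no effect size, standard deviation, power or dropout rate.
- **Expected results.** Item 4 states what is expected for group A, then continues "It is expected that for group B and C", and then adds: "It is not clear if in group D time points of week 1, 2, and 3 will be any different from time point 0". Group D appears nowhere else.
- **Removals.** For subjects who meet the stopping criteria, item 4 says: "Data from these subjects will not be used in the analysis". It does not say whether they are replaced.
- **Screening and consent.** Items 4 and 11 mention "a baseline screening to determine if you are eligible for this study". Item 11 also says: "Each participant will be enrolled only after signing an informed consent".
- **Analysis.** Section I, item 13 fits dose as a three-level factor, makes three pairwise comparisons at 0.05/3 = 0.017, and compares adverse events across three groups.

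**The concern.** The total number of subjects and the number of groups are basic design figures: the IRB approves them and staff recruit to them. Here they disagree. The enrolment target exceeds the defined groups by 15 people, and the text does not say whether those 15 would be screened only, given placebo or given digoxin. They are healthy volunteers for whom the protocol expects no direct benefit, and it lists digoxin toxicity among the risks.

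The group D sentence adds to the difficulty. The expected results run over A, B, C and D, but only A, B and C exist, so the stated expectations cannot be matched to the design.

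It is also unclear whether 15 per group means enrolled or evaluable, because removed subjects are dropped from the analysis. That question would exist even if the total read 45, but it has to be answered before the total can be stated properly.

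The concern does not rest on power, since the plan states none.

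**Working it through.** **Inputs.** Total recruited 60 (I.6). Targeted enrolment 60 (III.1). Three groups of 15 (I.4). Three dose levels and three pairwise comparisons (I.13). Group D: no dose and no size (I.4). Allowance for screen failure, dropout or replacement: none stated.

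**Step 1: can 60 be reproduced from the groups?**

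- 3 × 15 = 45, not 60.
- 60 − 45 = 15 subjects unaccounted for.
- 15/45 = 33% above the sum of the groups; 15/60 = 25% of the stated total.

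**Step 2: does the analysis section agree with the group list?** Three groups give 3 × 2/2 = 3 pairs, and 0.05/3 = 0.017, which is the plan's own threshold. Item 13 therefore agrees with the three-group list and is not part of the error.

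**Step 3: would an ordinary loss allowance give 60?** Using 45/(1 − d), rounded up:

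| Loss d | Total needed |
|---|---|
| 5% | 48 |
| 10% | 50 |
| 15% | 53 |
| 20% | 57 |
| 25% | 60 |
| 30% | 65 |

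Of these, only 25% gives 60. The simpler form 45 × (1 + d) needs d = 1/3. Neither figure is in the plan.

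**Step 4: what each possible reading of 60 implies.**

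| Reading | Arithmetic | Given digoxin | Difficulty |
|---|---|---|---|
| Fourth group of 15 | 4 × 15 = 60 | 30 if it does not receive digoxin; 3 × 15 = 45 if it does | Group not defined; the analysis has three groups |
| 20 per group | 60/3 = 20 | 2 × 20 = 40 | Contradicts n=15; group D unexplained |
| 15 screen failures | 60 − 15 = 45 assigned | 2 × 15 = 30 | Allowance not stated; group D unexplained |
| 15 replacements for removed subjects | 45 + 15 = 60 | 30 to 30 + 15 = 45, depending on the groups they enter | No replacement rule; group D unexplained |

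**Step 5: effect on the analysis if a fourth group were real.** The pairs would rise to 4 × 3/2 = 6 and the corrected threshold would become 0.05/6 = 0.0083 in place of 0.017.

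**The case against.** The best counter-argument is that 60 and 45 measure different things. Item 6 speaks of recruitment and Section III of targeted enrolment; neither says that 60 people will be assigned or dosed. Recruiting more than are assigned is normal. The eligibility rules (normal creatinine and EKG, no electrolyte abnormality, no medication) make some screening loss likely. Item 11 also allows someone already called a participant to be excluded for a reported digoxin allergy. The only defined digoxin places are the 30 in B and C, so the higher exposure counts are hypothetical. Group D is a single sentence on which no test depends.

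Much of this is fair. The screening reading is plausible, and the problem is an internal inconsistency more than a miscalculation. But plausible is not stated. No allowance is given, and a 25% loss would have to be assumed. Item 11 makes consent a precondition for enrolment without fixing when enrolment happens, so it permits the screening reading but does not establish it. That reading also leaves group D unexplained. If group D is only a stale label, it still has to be corrected, and the 60 still has to be accounted for.

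The objection is also right that the three-group model and threshold are sound as they stand. They would change only if a fourth group is intended.

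**Conclusion.** The concern holds. The stated total of 60 exceeds the sum of the defined groups by 15 subjects (33% of 45), nothing in the documents accounts for them, and group D is undefined. The number given digoxin could be anywhere from 30 to 45, depending on what 60 means.

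The shortfall of 15 assumes only that n=15 is the size of each group, as the group list says. That 4 × 15 equals 60 exactly, alongside a mention of group D, suggests a four-group design, but that is an inference and the documents do not say so. No claim is made about power, or about which groups or doses are right. Because the total and the number of groups are figures the trial relies on, this should be corrected and not left to interpretation.

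**What to change.** Reconcile Section I, items 4, 6 and 13, and Section III, item 1, to one design. The investigator should say what was meant.

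- **If three groups stand:** restate the total in I.6 and III.1 as 45 assigned, or as 45 assigned or evaluable with a stated maximum consented or screened (up to 60, if that was the intention) and a replacement rule. In I.4, say whether 15 per group means enrolled or evaluable. State which group the group D sentence refers to, then relabel or delete it so that the expectations match A, B and C.
- **If a fourth group is intended:** define it in the group list and carry it through the model, the adverse-event comparisons and the pairwise correction (six comparisons, 0.05/6 = 0.0083).

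**Cost.** With three groups: wording changes in I.4, I.6 and III.1 and an IRB modification, with no added subjects and no change to the model or threshold. With a fourth group: the analysis text in I.13 must be revised as well, including the corrected threshold.
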